Study Design: This is an open-label, dose-escalation Phase I clinical study conducted in patients with advanced solid tumors, aiming to evaluate the safety, tolerability, PK/PD characteristics, and preliminary efficacy of CNSI-Fe intratumoral injection in patients with advanced solid tumors.

Study Period: The study includes a screening period, a treatment period (including DLT evaluation period), and a follow-up period.

Screening Period: -28 to -1 days, to confirm that the subjects meet the inclusion criteria and do not meet the exclusion criteria.

Treatment Period (including DLT Evaluation Period): The DLT evaluation period is the first treatment cycle (duration: 21 days). During the DLT evaluation period, all subjects will receive CNSI-Fe intratumoral injection according to the protocol plan (preferentially selecting 1 suitable lesion for injection, tentatively with 1 injection on Day 1; if the corresponding dose of the investigational drug cannot be completed in 1 lesion, other lesions can be injected simultaneously; the dosing regimen may be adjusted by the sponsor and investigator based on the PK characteristics of this study). Safety assessments will be performed on Day 7, Day 14, and Day 21 after the first dose to evaluate DLT.

After the DLT evaluation is completed, subjects who do not experience unacceptable toxicity, if the investigator judges that the benefit of continued treatment outweighs

the risk, will enter the maintenance treatment period. In the maintenance treatment period, subjects will continue to receive one more dose of the investigational drug according to the DLT evaluation period dosing regimen (injection into the same lesion as the DLT evaluation period, tentatively with 1 injection on Day 1, the dosing regimen may be adjusted by the sponsor and investigator based on the PK characteristics of this study), and safety assessments will be performed on Day 7, Day 14, and Day 21 after dosing. Samples will be collected at the predetermined timepoints according to the study flow chart.

Follow-up Period: Safety follow-up until 28 days after the last dose.

Dose Escalation

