After the DLT assessment is completed, subjects who do not experience unacceptable toxicity, if the investigator judges that the benefit of continued treatment outweighs the risk, will enter the maintenance treatment period. During the maintenance treatment period, subjects will continue to receive the investigational drug according to the DLT assessment regimen (tentatively, one intratumoral injection on Day 1, the dosing regimen may be adjusted based on the PK characteristics of this study, as discussed by the sponsor and investigator).

Dose Groups: Three dose groups are tentatively set, namely 30 mg, 60 mg, and 90 mg (calculated as Fe^{2+}). Subsequently, based on the safety, tolerability, PK/PD, and preliminary efficacy data of CNSI-Fe, additional doses may be added for further investigation.

Research Steps: Please refer to the experimental process flow chart

Sample collection: PK and PD studies will be conducted by a designated third-party laboratory. The sampling time points for each sample may be adjusted based on the results of the previous clinical studies (decided by the SRC discussion). The methods for sample collection, processing, preservation, transportation, and testing will be described in a separate laboratory operations manual.

PK samples

First cycle: Within 1 hour before CNSI-Fe dosing, 5 min \pm 1 min, 10 min \pm 2 min, 15 min \pm 2 min, 30 min \pm 5 min, 1 h \pm 10 min, 2 h \pm 10 min, 4 h \pm 15 min, 8 h \pm 15 min, 12 h \pm 30 min, 24 h \pm 30 min, 48 h \pm 1 h, 72 h \pm 2 h after CNSI-Fe dosing.

Second cycle (if any): The sampling time points may be adjusted appropriately based on the PK results from the first cycle (adjusting sampling time, increasing/decreasing sampling frequency, etc.).

Collect 3 mL of blood sample at each sampling point.

PD samples (exploratory tumor tissue samples)

Before the first CNSI-Fe dose, 24 h to 17 days after the first CNSI-Fe dose (specific time points to be determined based on clinical practice), and at disease progression.

Subject to the subject's willingness, try to collect tumor tissue samples from the injected lesion before and after the first CNSI-Fe dose; the pre-dose tumor tissue sample can be the most recent archived sample or the sample collected during the screening period; post-dose tumor tissue samples will be collected according to clinical practice.

Tumor PK samples (exploratory tumor tissue samples)

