Before the first CNSI-Fe dose, within 21 days after the first CNSI-Fe dose (specific time points to be determined based on clinical practice).

Subject to the subject's willingness, try to collect tumor tissue samples from the injected lesion before and after the first CNSI-Fe dose; the pre-dose tumor tissue sample can be the most recent archived sample or the sample collected during the screening period; post-dose tumor tissue samples will be collected according to clinical practice as much as possible to complete the tumor PK study (not a mandatory requirement).

Statistical Analysis: Analysis of the Data Set

Full Analysis Set (FAS)

The FAS includes all enrolled subjects who received at least one dose of the study drug and had a measurable lesion at baseline.

Dose-Limiting Toxicity (DLT) Analysis Set (DLTS)

The DLTS includes subjects who completed the DLT evaluation period as per the protocol (defined as receiving at least one dose of the study drug at $\geq 80\%$ of the protocol-specified dose and did not prematurely discontinue or experience a DLT during the DLT evaluation period).

Safety Analysis Set (SS)

The SS includes all subjects who received at least one dose of the study drug and had at least one post-dose safety assessment.

Pharmacokinetic (PK) Analysis Set (PKS)

The PKS includes all subjects who received at least one dose of the study drug and had at least one valid PK measurement.

Pharmacodynamic (PD) Analysis Set (PDS)

The PDS includes all subjects who received at least one dose of the study drug and had at least one valid PD endpoint measurement.

Statistical Analysis Methods

The Statistical Analysis Plan (SAP) will provide detailed specifications and descriptions of all planned statistical analyses in accordance with the protocol, and will be finalized prior to database lock.

The statistical analyses will include demographic and baseline characteristics, safety and tolerability, PK, PD, and efficacy.

The analyses will be primarily descriptive, without formal statistical hypothesis testing.

The statistical analyses will be performed using SAS® version 9.4 or higher.

The following descriptive statistical analyses will be conducted based on the nature of the variables:

Continuous variables: number of non-missing observations, mean and standard deviation (SD), median, minimum, and maximum.

Categorical variables: frequency and percentage.

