Safety Analysis: For the primary estimand, the number of subjects, incidence, and number of events of each type of adverse event will be summarized by dose group.

Numerical laboratory data at each visit will be described using mean, SD, median, extremes, and changes from baseline, and categorized as normal, clinically insignificant abnormal, or clinically significant abnormal, with the incidence of clinically significant abnormalities tabulated. The same approach will be used for ECG. Vital signs will be described using mean \pm SD.

For the secondary estimand, the incidence of DLTs will be summarized by dose

group.

PK Analysis: The primary PK endpoints for CNSI-Fe intratumoral injection will include the iron ion concentration in serum. PK analyses will provide descriptive statistics of the relevant measurements and concentration-time profiles. For the first dose of CNSI-Fe, AUC, Cmax, Tmax, and other parameters may be calculated. Descriptive statistics will be provided for these parameters, and informal testing of AUC may be performed to explore the relationship with dose.

Efficacy Analysis: Based on best lesion response, ORR, DCR, and their two-sided 95% confidence intervals (Clopper-Pearson method) will be statistically described.

PD Analysis: Descriptive statistics will be provided for the PD endpoint levels before and after dosing, as well as the changes (absolute or percent) from baseline. Corresponding time course profiles will be generated. Comparisons of the PD endpoint levels and changes from baseline at each timepoint will be performed, with normality testing and using paired t-tests or Wilcoxon signed-rank tests as appropriate.

Research on time:

After this study has been reviewed and approved by the Ethics Committee (EC), it

will continue until the expected sample size is reached, based on the actual situation.

The study is expected to end 28 days after the last participant receives a maximum of two doses. For participants who still achieve CR (complete response) or PR (partial response) at the end of the study, if the investigator determines that they can still benefit from continued treatment, they can receive the study drug free of charge until disease progression, development of intolerable toxicity, the investigator determines it is no longer appropriate for the participant to continue receiving the study drug, or the sponsor terminates the study.

Table 1-1. Clinical Trial Flow Diagram

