Note: Unless otherwise specified, all assessments, examinations, and sample collections should be performed on the same day before drug administration.

Screening Period: Routine examinations or examination results obtained at a tertiary hospital (or this hospital) within 28 days prior to the first dose (unless otherwise specified) and before signing the informed consent form (ICF) can be used for screening, and do not need to be repeated.

Treatment Period (DLT Evaluation Period): For the first intratumoral injection of CNSI-Fe, safety assessments will be performed on Day 7 (± 1 day), Day 14 (± 1 day), and Day 21 (± 1 day) after the first dose to evaluate DLT.

Maintenance Treatment Period: After the DLT evaluation is completed, subjects without unacceptable toxicity will continue to the maintenance treatment period if the investigator determines that the benefit of continued treatment outweighs the risk. During the maintenance treatment period, subjects will receive one more dose of the investigational drug (intratumoral injection to the lesion, tentatively scheduled for Day 1, the dosing regimen may be adjusted based on the PK characteristics of this study by the sponsor and investigator).

Early Termination/End of Treatment (EOT) Visit: This will be scheduled within 7 days after the decision to discontinue treatment. If the assessments required for the

EOT visit were performed within 7 days prior to the EOT visit, they do not need to be repeated.

Safety Follow-up: Subjects who have received at least one dose of the study drug will undergo a safety visit 28 days (± 3 days) after the last dose. If the assessments required for the safety visit were performed within 3 days prior to the safety visit, they do not need to be repeated.

Medical History and Treatment History: Collected during the screening period, including past medical history, medication history (concomitant treatments within 4 weeks prior to screening and currently ongoing), history of all previous tumors (including tumor stage, diagnosis date, genetic test results), history of all previous anti-tumor treatments, family history, surgical history, immunization history, allergy history, smoking history, alcohol history, history of drug abuse/dependence, etc.

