Adverse Events (AEs): Only serious adverse events (SAEs) related to the protocol-specified procedures should be reported before the start of study drug treatment. After the start of study treatment, all AEs should be reported, regardless of their relationship to the study drug, until 28 days after the last dose. The investigator should follow up on all AEs until the event resolves to baseline or better, is considered stable by the investigator, the subject is lost to follow-up, or the subject withdraws consent. For all SAEs related to the investigational product or study procedures, every effort should be made to follow up until a final outcome can be reported.

Blood routine: Red blood cell count (RBC), hemoglobin (Hb), hematocrit, white blood cell count (WBC) and differential count (neutrophils, eosinophils, lymphocytes, monocytes, basophils and others) and platelet count (PLT). To be performed within 7

days prior to first dose of study drug in the screening period, on Day 7, Day 14, Day 21 of each cycle, at the End of Treatment (EOT) visit, and at the safety follow-up visit (excluding telephone visits). Additional blood routine tests can be performed as needed based on the investigator's clinical judgment.

Urinalysis: Urine specific gravity, urine pH, urine glucose, urine protein, urine ketone, urine red blood cells and urine white blood cells. To be performed within 7 days prior to first dose of study drug in the screening period, on Day 7, Day 14, Day 21 of each cycle, at the EOT visit, and at the safety follow-up visit (excluding telephone visits).

Biochemistry: Glucose, blood urea nitrogen (BUN) or urea, creatinine (Cr), sodium, potassium, magnesium, chloride, calcium, phosphorus, total bilirubin (TBIL), alanine aminotransferase (ALT), aspartate aminotransferase (AST), alkaline phosphatase (ALP), lactate dehydrogenase (LDH), total protein, albumin, triglycerides, total cholesterol, amylase, lipase. To be performed within 7 days prior to first dose of study drug in the screening period, on Day 7, Day 14, Day 21 of each cycle, at the EOT visit, and at the safety follow-up visit (excluding telephone visits). Additional biochemistry tests can be performed as needed based on the investigator's clinical judgment.

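### By-dose AE incidence and event counts have no stated window or exposure denominator, although Cycle 1 tolerability helps decide who gets a second injection and longer observation

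*Combined protocol and SAP*

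**What the plan says.** The AE analysis is one sentence under Safety Analysis, labelled as serving the primary estimand: "the number of subjects, incidence, and number of events of each type of adverse event will be summarized by dose group". No window, cycle, number of injections or person-time is attached to it.

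Four other places fix what that sentence would summarize:

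- **Collection window** (Table 1-1 notes, Adverse Events): after treatment starts, "all AEs should be reported, regardless of their relationship to the study drug, until 28 days after the last dose".
- **Who is re-dosed** (Table 1-1 notes, Maintenance Treatment Period): "subjects without unacceptable toxicity will continue to the maintenance treatment period if the investigator determines that the benefit of continued treatment outweighs the risk". The Study Period and Maintenance Treatment Period sections of the synopsis say the same.
- **How much more drug** (same note): "subjects will receive one more dose of the investigational drug". Under Research on time: "The study is expected to end 28 days after the last participant receives a maximum of two doses".
- **Denominator** (Safety Analysis Set): "The SS includes all subjects who received at least one dose of the study drug and had at least one post-dose safety assessment". Subjects with one injection and subjects with two fall in the same set.

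Two safety summaries do have fixed time points. DLT incidence by dose group is tied to the 21-day first cycle, and laboratory and ECG data are described by visit.

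**The concern.** The length of AE follow-up and the number of injections are partly consequences of the toxicity being measured. A dose that is hard to tolerate sends fewer subjects to the second injection, so its group contributes fewer injections and fewer days in which an AE can be counted. A well tolerated dose contributes more of both. Incidence and event counts per dose group then mix the effect of dose with the amount of exposure, and the mixing tends to narrow the difference between a tolerable dose and a less tolerable one.

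AEs are part of the primary endpoint, and the primary objective is to give a basis for choosing doses in later studies. If escalation ends without reaching an MTD, DLT counts will separate the doses poorly, and readers will lean on the ordinary AE profile.

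**Working it through.** The plan gives no AE rate, re-dosing rate or precision target for this point, so there is no figure of its own to reproduce. The check is an illustration with assumed rates.

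**Inputs from the documents.** AE collection runs to 28 days after the last dose (Table 1-1 notes). Cycle 1 lasts 21 days (Study Period). There are at most two injections within the study (Research on time).

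**Assumptions.** The AE hazard is constant, giving 30% by day 28 at the lower dose and 1.5 times that hazard at the higher dose. The AE type is unrelated to the reason for stopping. The second injection is given as soon as the 21 days are over. All lower-dose subjects are re-dosed; a share q of higher-dose subjects is.

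**Step 1: observation time.** One injection: 28 days. Two injections: at least 21 + 28 = 49 days. Ratio: 49/28 = 1.75. If only subjects with a DLT are not re-dosed, the mean is 28 + 21q days:

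- no DLT: q = 1, 49 days
- 2 of 6 with DLT: q = 2/3, 42 days
- 2 of 3 with DLT: q = 1/3, 35 days

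**Step 2: incidence over all collected follow-up.** Incidence over t days at hazard ratio h is 1 − 0.70^(h·t/28).

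- Lower dose, 49 days: 1 − 0.70^1.75 = 46.4%
- Higher dose, not re-dosed, 28 days: 1 − 0.70^1.5 = 41.4%
- Higher dose, re-dosed, 49 days: 1 − 0.70^2.625 = 60.8%

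The higher-dose group as a whole shows 41.4% + q × 19.4 points.

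| Share of higher dose re-dosed | Lower dose | Higher dose | Difference (points) |
|---|---|---|---|
| none | 46.4% | 41.4% | −5.0 |
| one third | 46.4% | 47.9% | +1.5 |
| two thirds | 46.4% | 54.3% | +7.9 |
| all | 46.4% | 60.8% | +14.4 |

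The order reverses only if q is below 5.0/19.4, about 0.26. At one third the order is kept, but a 14.4-point difference under equal exposure has shrunk to 1.5.

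**Step 3: fixed window.** To Day 21 the lower dose shows 1 − 0.70^0.75 = 23.5% and the higher dose 1 − 0.70^1.125 = 33.1%, whatever q is.

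**Step 4: when the AE is itself what stops treatment.** Let p = 0.4 be its chance per injection, with everyone else re-dosed. Subject-level incidence is 1 − 0.6² = 64%, the same as if all had received two injections, because those who stopped are already counted. Events per subject are 0.4 + 0.6 × 0.4 = 0.64, against 0.80 under equal exposure. Only the event count is lowered.

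**Step 5: AEs correlated with the stopping toxicity.** This was simulated with 400,000 subjects per setting. Nominal per-injection AE risk was 0.30 at the lower dose and 0.40 at the higher; stopping toxicity was 0.05 and 0.60. Incidence over both cycles came out at about 50% in both groups at every strength of correlation tried. With two injections for everyone it would be 51–52% against 59–64%. Correlation of this kind does not remove the flattening.

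**Step 6: precision.** With six subjects, the exact 95% interval for 3/6 is 12% to 88%.

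**The case against.** A reader might infer three stronger things, and the documents support none of them.

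*That the plan prescribes a whole-study table.* It does not say so. The window is inferred from the collection period and the absence of any restriction. The protocol leaves detail to an SAP to be finalized before database lock, and the text reviewed ends partway through the Table 1-1 notes, so a window may be set elsewhere. As written, though, the sentence does not limit what is counted.

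*That the table will understate toxicity at poorly tolerated doses, or put doses in the wrong order.* Neither is certain. Incidence of the toxicity that stops treatment is not lowered (step 4). Reversal needs q below about 0.26, while the 3+3 stopping boundaries alone give q of one third or two thirds. The benefit judgement and other reasons for not re-dosing could lower q further, but the documents give no rate.

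*That escalation or the MTD is biased.* These rest on first-cycle DLTs, with 21 days for everyone evaluated, and are untouched.

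It is also fair that the analysis is descriptive, that groups of 3 to 6 make chance variation larger than this distortion, and that the two-injection limit bounds the imbalance. The limit is not entirely firm: the Dosing Volume section allows unplanned doses, and responders may continue after study end. Small numbers also do not excuse a systematic distortion that a table layout can avoid. The DLT table is only a partial substitute: it covers a narrow set of events, and the DLT set is worded so that it can be read as leaving out subjects with a DLT. Finally, a Cycle 1 table alone would hide toxicity from repeat injection, so the cumulative table should stay.

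**Conclusion.** The concern holds as a problem of comparison between doses. Taken as written, the by-dose AE summary pools subjects with one injection and about 28 days of observation with subjects who have two injections and at least 49 days, and Cycle 1 tolerability is one of the things that sorts them. Event counts, and incidence of AE types other than the stopping toxicity, can be diluted at a poorly tolerated dose relative to a well tolerated one.

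Under the assumed rates, the dilution takes a 14.4-point difference to 7.9 points with two thirds of the higher dose re-dosed and to 1.5 points with one third. Only a nearly complete failure to re-dose reverses the order. These sizes depend on a constant hazard and on rates that the documents do not supply, so they show what can happen and do not predict it. The change is worth making because it concerns a primary safety endpoint and costs little.

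**What to change.** Keep the cumulative by-dose AE table, and specify in the SAP:

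1. A by-dose Cycle 1 table of AEs with onset from the first injection to Day 21 or the second injection, whichever is earlier, among all dosed subjects. Name this as the table for comparing dose groups.
2. A separate by-dose table of AEs with onset after the second injection, with re-dosed subjects as the denominator.
3. For each dose group, the number re-dosed, the reasons for not re-dosing, and subject-days at risk.

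State the window of the cumulative table explicitly. AEs that start after Day 21 in subjects not re-dosed will appear only there.

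The cost is SAP wording and a few tables from data already collected, with no change to treatment or visits. Withdrawal reasons already go into the eCRF; check that the reason for withholding the second injection is also captured for subjects who remain in the study. The second-injection table will have very small denominators and should be read as a listing with counts.

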The basis for dose selection: According to the "Guidance Principles for Estimating the Maximum Recommended Starting Dose for First-in-Human Clinical Trials of Healthy Adult Volunteers" issued by the NMPA, and with reference to the Maximum Recommended Starting Dose (MRSD) for anticancer drugs in ICH S9 "Nonclinical Evaluation for Anticancer Pharmaceuticals", the design of the dosage regimen depends on the data from the long-term toxicity studies of CNSI-Fe in animals. In the toxicity study with 2 intramuscular injections on Day 1 and Day 4, followed by a 4-week recovery period in rats, the Highest Non-Severely Toxic Dose (HNSTD) was 20 mg/kg (calculated as Fe²⁺), corresponding to a Human Equivalent Dose (HED) of 3.6 mg/kg; in the toxicity study with Beagle dogs, the HNSTD was 15 mg/kg, corresponding to an HED of 8.7 mg/kg. Assuming an adult body weight of 60 kg and a safety factor of 6, the MRSD for humans is estimated to be approximately 0.6

mg/kg and 1.45 mg/kg, respectively.

Considering the effective doses in preclinical studies, in multiple solid tumor xenograft models (human colon cancer COLO 205, human breast cancer MDA-MB-231, human breast cancer HCC1954, and human colon cancer HT-29 cells), CNSI-Fe (calculated as Fe²⁺, 0.1875 mg, 0.375 mg, 0.50 mg, 0.75 mg, administered twice on Day 1 and Day 4) significantly inhibited tumor growth. The effective dose and the maximum effective dose were 0.1875 mg and 0.75 mg, respectively. Assuming a mouse body weight of 20 g and an adult human body weight of 60 kg, the corresponding human equivalent doses are 0.84 mg/kg and 3.36 mg/kg, respectively.

Considering the above factors and the safety of the first-in-human trial, this study selected 0.5 mg/kg as the starting dose, with escalating doses of 0.5 mg/kg, 1.0 mg/kg, and 1.5 mg/kg. Calculated based on an average human body weight of 60 kg, the escalating doses are 30 mg, 60 mg, and 90 mg (calculated as Fe²⁺). If ≥2 subjects experience DLT at the 90 mg dose, the dose will be reduced to 75 mg for safety and tolerability observation; if the dose escalation to 90 mg does not reach the MTD, the SRC will discuss whether to further escalate the dose to 120 mg, 150 mg, or even higher, based on the available safety, PK/PD, and preliminary efficacy data (if 120 mg still does not reach the MTD, the SRC will discuss whether to stop the dose escalation or directly proceed to 150 mg or even higher doses).

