This study will enroll patients with advanced solid tumors and use the traditional "3+3 method" for dose escalation. The dose escalation principle is: in any dose cohort, 3 subjects will be enrolled first. If none of the first 3 subjects experience DLT during the DLT evaluation period, the next dose cohort can be entered. If ≥ 2 of the first 3 subjects experience DLT during the DLT evaluation period, dose escalation will be stopped (for the 30 mg cohort, if 2 DLTs occur, the sponsor and investigator will jointly decide whether to reduce the dose and continue exploration). If 1 of the first 3 subjects experiences DLT during the DLT evaluation period, an additional 3 subjects will be enrolled in that dose cohort, and if ≤ 1 of the 6 subjects in that dose cohort experience DLT during the DLT evaluation period, the next dose cohort can be entered; if ≥ 2 of the 6 subjects in that dose cohort experience DLT during the DLT

evaluation period, dose escalation will be stopped. The dose prior to the dose at which $\geq 2/3$ or $\geq 2/6$ subjects experience DLT during the DLT evaluation period will be determined as the MTD (if only 3 subjects are enrolled in a cohort, an additional 3 subjects will need to be enrolled).

The “3+3” dose escalation principle

The number of subjects who experienced a dose-limiting toxicity (DLT) within a particular dose cohort	dose escalation principle
0/3	no DLT is observed in the 3 newly enrolled subjects
0/3	no DLT is observed in the 3 newly enrolled subjects
$\geq 2/3$	Dose escalation should be stopped, and that dose will be considered the Maximum Administered Dose (MAD). If the previous lower dose was only administered to 3 subjects, then 3 more subjects need to be enrolled
1/3	
If the 3 newly enrolled subjects in the dose group do not experience a DLT (Dose-Limiting Toxicity), then the study will proceed to the next dose group.
 
 ● ● If ≥ 1 of the 3 newly enrolled subjects in the dose group experience a DLT, then dose escalation will be stopped, and that dose level will be considered the MAD (Maximum Administered Dose). The previous dose level will be considered the MTD (Maximum Tolerated Dose) (if the dose group only had 3 subjects, then an additional 3 subjects will need to be enrolled).

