The DLT (Dose-Limiting Toxicity) evaluation period is in the first cycle, i.e., within 21 days after the first dose. This stage is tentatively set with 3 dose groups (calculated as Fe^{2+} , 30 mg, 60 mg, 90 mg). If ≥ 2 subjects in the 90 mg group observe DLT, the dose will be reduced to 75 mg for safety and tolerability observation; if the dose is increased to 90 mg and MTD (Maximum Tolerated Dose) is still not reached, the SRC

(Safety Review Committee) will discuss continuing to escalate the dose to 120 mg, 150 mg, or even higher (if MTD is still not reached at 120 mg, the SRC will discuss whether to stop dose escalation or directly proceed to 150 mg or even higher doses).

After 3-6 subjects in each dose group have completed the DLT evaluation, the SRC will evaluate the overall safety of each dose group based on the data obtained and determine whether to continue escalating to the next dose group or to determine the recommended dose for subsequent clinical development.

Enrollment Interval: To fully protect the safety of the subjects, during the dose escalation process, the first subject in each dose group must be dosed at least 3 days after the first dose, and the remaining subjects in that dose group can then start the first dose. The interval for subsequent subjects in the same dose group can be controlled at the discretion of the investigator. The last subject in each dose group must complete the DLT evaluation, and the safety and tolerability must be reviewed by the SRC before the first subject in the next dose group can receive the first dose.

Subject Replacement: During the DLT evaluation period, if a subject is unable to be evaluated for DLT (e.g., the subject's dose of the study drug did not reach at least 80% of the protocol-specified dose, or the subject discontinued study treatment before completing the DLT evaluation period for reasons other than DLT), additional subjects will need to be enrolled to make up the corresponding number in that dose

group.

DLT Definition: This study will grade toxicities according to NCI CTCAE v5.0. DLT refers to the following toxicity reactions that are considered by the investigator and/or the sponsor to be definitely or possibly related to the study drug CNSI-Fe, occurring within the first cycle (i.e., within 21 days after the first dose):

Hematological toxicity:

- (1) Any grade 4 hematological toxicity;

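### DLT incidence, a primary endpoint, gets only a by-dose summary while ORR and DCR get exact intervals, although the recommended dose may rest on 0/3 DLTs (upper 95% limit 70.8%)

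*Combined protocol and SAP*

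**What the plan says.** **Endpoint status.** The Study Endpoints section of the synopsis places DLT incidence under the primary endpoints. ORR and DCR appear under the secondary endpoints.

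**Analysis.** Under Safety Analysis the whole provision for DLTs is "For the secondary estimand, the incidence of DLTs will be summarized by dose" group. The general list under Statistical Analysis Methods gives counts and percentages for categorical variables. Under Efficacy Analysis, ORR and DCR are treated differently: "their two-sided 95% confidence intervals (Clopper-Pearson method) will be statistically described".

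**Escalation.** Under Dose Escalation, a clean first cohort is enough to move up: "If none of the first 3 subjects experience DLT during the DLT evaluation period, the next dose cohort can be entered". The dose below one stopped for DLTs becomes the MTD, and for that dose "if only 3 subjects are enrolled in a cohort, an additional 3 subjects will need to be enrolled".

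**Recommended dose.** The same section says: "After 3-6 subjects in each dose group have completed the DLT evaluation, the SRC will evaluate the overall safety of each dose group", and on that basis the committee is to "determine whether to continue escalating to the next dose group or to determine the recommended dose for subsequent clinical development". If no MTD has appeared, the dose-selection rationale leaves the next step to discussion: "if 120 mg still does not reach the MTD, the SRC will discuss whether to stop the dose escalation". No minimum number of subjects is given for the highest dose on that path. The primary objective accepts a maximum injectable dose in place of an MTD, again with no number of subjects or DLT rule attached.

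**Analysis set.** The DLT analysis set is defined by receipt of at least 80% of the planned dose and by completing the evaluation period without early discontinuation or a DLT.

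**The concern.** The stated purpose of the primary objective is to support dose selection in later studies. The rate that bears most directly on that purpose is reported with no measure of uncertainty, while response rates from the same small cohorts get exact limits.

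The gap matters most when escalation ends without an MTD. A dose named MTD must have six subjects. A top dose that was never stopped for DLTs has no such condition, so its DLT record may be three subjects with no event. Printed as a count and percentage, that is 0 of 3, 0%. A reader planning the next trial sees a zero and no sign of how high the DLT rate could be.

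The analysis set adds to this. Its wording can be read as removing subjects who had a DLT. On that reading the numerator is zero by construction, and an interval calculated on that set would be misleading.

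**Working it through.** **The plan's only sample-size figure.** The maximum is 30 subjects. Five upward dose levels are named (30, 60, 90, 120 and 150 mg), and 5 × 6 = 30, which reproduces the maximum. The documents do not state this derivation, so it is inferred. No target DLT rate, alpha or power is given.

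**Inputs.**
- Passing results at a dose (Dose Escalation): 0/3, or 1/3 followed by 0/3, that is 1/6.
- Number of subjects before the committee may set the recommended dose (Dose Escalation): 3 to 6.
- Number of subjects at a dose named MTD (Dose Escalation): 6.
- Interval method and level (Efficacy Analysis): Clopper-Pearson, two-sided 95%.

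**Formulas.** For x = 0, the lower limit is 0. The upper limit is 1 − 0.025^(1/n) two-sided, or 1 − 0.05^(1/n) one-sided. For x = 1, the two-sided upper limit is the rate p that solves (1−p)^n + n·p·(1−p)^(n−1) = 0.025 (0.05 for the one-sided limit). The lower limit is 1 − 0.975^(1/n).

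**Results.**
- 0/3: 1 − 0.025^(1/3) = 1 − 0.2924 = 0.7076; one-sided 1 − 0.05^(1/3) = 1 − 0.3684 = 0.6316.
- 0/6: 1 − 0.025^(1/6) = 1 − 0.5407 = 0.4593; one-sided 1 − 0.05^(1/6) = 1 − 0.6070 = 0.3930.
- 1/6: lower 1 − 0.975^(1/6) = 0.0042; upper 0.6412. Check: 0.3588^6 + 6 × 0.6412 × 0.3588^5 = 0.0021 + 0.0229 = 0.025. One-sided upper 0.5818.

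| DLTs | Two-sided 95% interval | One-sided 95% upper limit |
|---|---|---|
| 0/3 | 0 to 70.8% | 63.2% |
| 0/6 | 0 to 45.9% | 39.3% |
| 1/6 | 0.4% to 64.1% | 58.2% |

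These limits need no assumption about the true DLT rate.

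**Effect of the analysis-set wording.** Take a cohort with 1 DLT in 6. If the subject with the DLT is dropped, it becomes 0/5, with upper limit 1 − 0.025^(1/5) = 1 − 0.4782 = 52.2% in place of 64.1%, and an observed rate of 0% in place of 16.7% (1/6).

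**The case against.** **The text is incomplete.** The available text stops within the tumour-assessment note to the flow table, refers to sections not included, and defers detail to a SAP to be finalized before database lock. A DLT interval or a minimum number at the top dose could be there. This stands: the point concerns what the available text specifies.

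**The summary rule is not exclusive.** A reader might infer that the plan confines DLTs to a count and percentage. It does not. ORR and DCR are categorical too, and they receive intervals on top of that rule. The supportable statement is that no interval is named for DLTs.

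**The committee sees more than DLTs.** A reader might infer that 0/3 alone fixes the recommended dose. The documents do not say so. The SRC reviews overall safety, the primary safety endpoints extend to adverse events, laboratory tests, vital signs and ECG, and going above 90 mg also draws on PK/PD and efficacy data. Three subjects are permitted, not prescribed, and the maximum of 30 leaves room for six at each of the five named levels. Nor does the plan prescribe any wording for a conclusion that no MTD was reached. None of this puts a limit on the DLT rate for those who use the result later.

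**The design itself.** It is tempting to argue that the trial too often passes toxic doses. If the true DLT rate were assumed to be one third, the 3+3 rule would pass the dose with probability (2/3)^3 + 3(1/3)(2/3)^2(2/3)^3 = 0.296 + 0.132 = 0.428. But the plan states no target rate and no hypothesis test, the figure includes six-subject passes, and it belongs to any design with this rule. Reporting an interval would not change it.

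**Six subjects are not precise either.** True: the upper limit for 1/6 is close to that for 0/3. That supports printing the limit and does not show that a larger cohort alone would settle the matter.

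**The interval is not exact here.** Clopper-Pearson assumes a fixed n, whereas this n depends on early outcomes and the reported dose is selected for few DLTs. This stands, and the limits should be called nominal.

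**Conclusion.** The point holds as a reporting gap in a primary endpoint. In the available text DLT incidence has no interval, while ORR and DCR do. Where no MTD is reached, the DLT evidence at the recommended dose may be 0/3, which leaves rates up to 70.8% (two-sided) or 63.2% (one-sided) compatible with the data. That limits what may be concluded about the dose carried forward. It does not invalidate the trial, and it is not evidence that any dose is unsafe.

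The size rests on two things: that the committee uses the permission to act on three subjects, and that the limits are read as nominal. It is conditional on any SAP or later protocol text that already specifies an interval.

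The conflict between the primary endpoint listing and the secondary estimand label in Safety Analysis is real. With no alpha or testing hierarchy, though, it alters no result and is a wording correction only.

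**What to change.** 1. In Safety Analysis, report DLTs as x/n per dose group with the two-sided 95% Clopper-Pearson interval already specified for ORR and DCR.
2. State that the denominator is every DLT-evaluable subject, including those who had a DLT, and reword the DLT analysis set so that it cannot be read as excluding them.
3. For whichever dose is named MTD, maximum injectable dose or recommended dose, give the upper limit beside any tolerability conclusion, with a note that it is nominal because cohort size depends on outcomes.
4. Align the estimand label with the endpoint list.
5. If pass probabilities are quoted in support, mark the true DLT rates as assumptions.

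The cost is a few lines of analysis text, one clarified definition and one column in a table. No further patients are needed, and the escalation rule and the doses are untouched. The downside is that the tolerability statement becomes visibly less favourable.
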